1.3. Schedule of Events

Table 1.1: Schedule of Events: Treatment Continuation Cohort

	Visits	SCR	BL	M3	M6	M9	M12	M15	M18	M21	EOT ^a	EOS/AE F/U ^b	Comment
	Window (Days)	0*	0*	±7	±7	±7	±14	±14	±14	±14	±7	±7	* SCR and BL will both occur on EOT visit of preceding study.
Assessments	Procedure												
Informed consent		X											Obtain prior to performing any study procedures
Eligibility assessment			X ^c										
Demographics/Medical history/Prior medications, non-drug therapies, and radiotherapy/Height	N/A												This information will be transferred from prior studies
Vitals	Vital signs and weight	X	X ^c	X	X	X	X	X	X	X	X		
PRO instruments	EQ-5D-5L		X ^c	X	X	X	X	X	X	X	X		Performed before any physical tests
	PROMIS PF		X ^c	X	X	X	X	X	X	X	X		Physical Function Scale performed before any physical tests
Safety	Physical exam	X	X ^c	X	X	X	X	X	X	X	X		Full PE on Screening and EOS, abbreviated PE at other visits. All PE exams will include functional assessment for the affected joint.
	ECG	X	X ^c								X		May be performed whenever deemed medically necessary and at any visit during which a subject exhibits a heart rate ≤50 bpm. Any abnormal finding should be confirmed with a repeated ECG. ECGs should be performed after vital signs assessments.

	Visits	SCR	BL	M3	M6	M9	M12	M15	M18	M21	EOT ^a	EOS/AE F/U ^b	Comment
	Window (Days)	0*	0*	±7	±7	±7	±14	±14	±14	±14	±7	±7	* SCR and BL will both occur on EOT visit of preceding study.
Assessments	Procedure												
AE	TEAE/SAE		X ^c					X			X		See Section 8.4.1
Concomitant medications, non-drug therapies, and radiotherapy	Concomitant		X ^c					X					
Laboratory assessments	Hematology		X ^c	X	X	X	X	X	X	X			See Section 10.2 for details
	Chemistry		X ^c	X	X	X	X	X	X	X			See Section 10.2 for details
	Urinalysis		X ^c		X		X		X		X		See Section 10.2 for details
	Coagulation		X ^c	X	X	X	X	X	X	X	X		See Section 10.2 for details
	Serum pregnancy test	X	X ^d								X		For females of reproductive potential (as defined in Section 5.1)
	Liver function tests		X	X	X	X	X	X	X	X	X		AST, ALT, ALP, total bilirubin, GGT, direct bilirubin
	Hormone testing		X ^c										Females only, FSH to confirm postmenopausal status
	TSH	X	X										
Treatment response/Disease assessment	MRI of affected joint		X ^c		X		X		X		X ^e		Tumor assessment. Additional imaging assessments may be performed with changes in tumor response(s), as deemed necessary by the Investigator.

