Dosing Diary	Provide Diary		X	X	X	X	X	X	X	X			Diary for pill count and AEs between scheduled clinic visits
	Review Diary			X	X	X	X	X	X	X	X		

	Visits	SCR	BL	M3	M6	M9	M12	M15	M18	M21	EOT ^a	EOS/AE F/U ^b	Comment
	Window (Days)	0*	0*	±7	±7	±7	±14	±14	±14	±14	±7	±7	* SCR and BL will both occur on EOT visit of preceding study.
Assessments	Procedure												
Study Drug: Pexidartinib	Dispense 3-month supply		X	X	X	X	X	X	X	X			
	Collect returned/Assess treatment compliance		X	X	X	X	X	X	X	X	X		
EOS Form												X	

AE = adverse event; BL = baseline; D = day; ECG = electrocardiogram; EOS = End of Study; EOT = End of Treatment; EQ-5D-5L = European Quality of Life Five Dimension Five Level Scale; FSH = follicle stimulating hormone; FU = Follow-up; M = month; MRI = magnetic resonance imaging; PRO = Patient-Reported Outcome; PROMIS PF = Patient-Reported Outcomes Measurement Information System – Physical Function; SAE = serious adverse events; SCR = screening; TEAE = treatment emergent adverse events; TVS = tumor volume score.

Note: For all visits, a month is considered a 30-day interval.

^a The EOT visit should occur within 7 days after the last dose of pexidartinib or at the time the decision is made to discontinue pexidartinib (if this is more than 7 days after the last dose of pexidartinib), unless there is a medical condition that prevents subjects from completing the visit within this time. The EOT visit must occur within 24 months after enrollment.

^b The End-of-Study will be reached with a follow-up phone call 1-month post-EOT visit to collect AE information.

^c Assessment does not need to be repeated if the procedure was done at End-of-Treatment visit of preceding study.

^d Urine pregnancy test at Screening only.

^e Only subjects who end their study participation early with no radiologic disease progression will have an additional MRI at 3 months ± 14 days after their last dose of study treatment or before any new TGCT therapy, including surgery, whichever occurs first. EOS will occur after this additional MRI.

Table 1.2: Schedule of Events: Treatment-Free Period of Treatment-Free/Re-Treatment Cohort

	Visits	SCR	BL	M1	M3/ M15	M6/ M18	M9/ M21	M12 ^a	M24	EOS/ AE F/U ^b	Comment
	Window (Days)	0*	0*	+ 28	±14	±14	±14	±14	±14	±7	** SCR and BL will both occur on EOT visit of preceding study.
Assessments	Procedure										
Informed consent		X									Obtain prior to performing any study procedures
Eligibility assessment			X								

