8.4. Safety Assessments

8.4.1. Adverse Event

Methods to Detect Adverse Events

The definitions of an AE, TEAE, and SAE can be found in Section 9.5.2 and Section 10.5. Adverse events may be directly observed, reported spontaneously by the subject or by questioning the subject (or, when appropriate, by a caregiver, surrogate, or the subject's legally authorized representative) at each study visit. Subjects should be questioned in a general way, without asking about the occurrence of any specific symptoms. Between scheduled clinic visits, subjects should be instructed to enter all AEs in their Diary. The Investigator must assess all AEs to determine seriousness, severity, and causality. The Investigator and any qualified designees are responsible for detecting, documenting, and recording events that meet the definition of an AE or SAE and remain responsible for following AEs that are serious, considered related to the study drug or study procedures, or that caused the subject to discontinue pexidartinib.

All clinical laboratory results, vital signs, and ECG results or findings should be appraised by the Investigator to determine their clinical significance. Isolated abnormal laboratory results, vital sign findings, or ECG findings (i.e., not part of a reported diagnosis) should be reported as AEs if they are symptomatic, lead to study drug discontinuation, lead to dose reduction, require corrective treatment, or constitute an AE in the Investigator's clinical judgment.

COVID-19 assessments are detailed in Section 8.4.4.

Time Period for Collecting Adverse Events, Serious Adverse Events

All serious adverse events (SAEs) occurring after the subject signs the ICF and up to 30 days after the last dose of study medication if applicable or EOS/FU visit, whether observed by the Investigator or reported by the subject, will be recorded on the AE eCRF. All SAEs will be followed until resolution, stabilization, the event is otherwise explained, or the subject is lost to follow-up.

All non-serious AEs occurring after the subject has taken the first dose of study medication/signs the ICF until 30 days after the last dose of study medication will be recorded on the AE eCRF.

Exacerbation of a pre-existing medical condition and symptom after the subject signs the ICF including increase in severity of the symptom will be recorded as an AE on the AE eCRF, unless it is a condition of TGCT.

Reporting Procedure for Investigators

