9.5.2. Safety Analyses

Safety analyses will be performed using the Safety Analysis Set and subjects will be analyzed by cohort separately.

Adverse Events

TEAEs are defined as new AEs or pre-existing conditions that worsen in CTCAE grade after the first dose of study drug and up to 30 days after last dose of study drug. AEs collected after 30 days after the last dose of study drug will not be considered TEAEs unless they are treatment related. AEs will be coded using the Medical Dictionary for Regulatory Activities (MedDRA) dictionary. An AE will be assigned to the study period in which it started, even if it resolved in a subsequent period. Incidence of TEAEs occurring over time, (e.g., 0 to 6 months, 6 to 12 months, etc.) will be summarized. The number and percentage of subjects reporting TEAEs will be calculated overall, by system organ class, by preferred term, and by cohort.

TEAEs will be further summarized by CTCAE grade and relationship to study drug. Similarly, the number and percentage of subjects reporting treatment-emergent SAEs and related treatment-emergent SAEs will be tabulated, and TEAEs leading to discontinuation of study drug.

A by-subject AE (including treatment-emergent) data listing including but not limited to verbatim term, preferred term, system organ class, CTCAE grade, and relationship to study drug will be provided. Deaths, other SAEs, AESIs, and AEs associated with study drug discontinuation, will be listed. AEs due to COVID-19 will be also summarized and listed.

Clinical Laboratory Evaluation

Descriptive statistics will be provided for the clinical laboratory results by scheduled time of evaluation and by cohort, as well as for the change from Baseline. The Baseline value is defined as the last non-missing value before the initial administration of study drug. In addition, mean change from Baseline will be presented for the maximum and minimum post-treatment values and the values at the EOT visit.

Abnormal clinical laboratory results will be graded according to NCI-CTCAE version 5.0, if applicable, and the grade will be presented in a by-subject data listing. A shift table, presenting by cohort the two-way frequency tabulation for baseline and the worst post-treatment value according to the CTCAE grade, will be provided for clinical laboratory tests. A listing of abnormal clinical laboratory test results deemed of clinical significance or of Grade 3 or 4 will be generated.

ECG

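### The Table 1.1 safety call can fall up to 7 days before the 30-day post-dose window closes, and the SAE cut-off for early leavers is not stated unambiguously

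*Combined protocol and SAP*

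**What the plan says.** **Timing of the last contact.** In Table 1.1 (Treatment Continuation Cohort), footnote b reads: "The End-of-Study will be reached with a follow-up phone call 1-month post-EOT visit to collect AE information". The window row gives the EOS/AE follow-up column ±7 days. The table note fixes the unit: "Note: For all visits, a month is considered a 30-day interval". Footnote a places EOT relative to dosing: "The EOT visit should occur within 7 days after the last dose of pexidartinib", or later if the decision to stop comes later.

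**Window to be covered.** Section 8.4.1 records non-serious AEs until 30 days after the last dose, and SAEs "up to 30 days after the last dose of study medication if applicable or EOS/FU visit". Section 9.5.2 defines TEAEs over the same 30 days and adds: "AEs collected after 30 days after the last dose of study drug will not be considered TEAEs unless they are treatment related". Table 3.2 lists the number of subjects with TEAEs under secondary objectives but labels it a primary outcome measure.

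**End of Study.** Footnote b ties it to the call. Footnote e of Table 1.1 (f in Table 1.3) covers subjects who stop early without radiologic progression. They have an extra MRI 3 months ± 14 days after the last dose, or before new TGCT therapy if that is sooner, and "EOS will occur after this additional MRI". Section 4.1.2 defines a subject's End of Study as the last visit or contact.

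**The concern.** The call is anchored to the EOT visit, but the safety window is anchored to the last dose. Nothing in Table 1.1 makes the call wait until the window has closed. An event that begins after an early call is then left to spontaneous reporting, in a measure the protocol labels a primary outcome.

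The second issue is the end of SAE collection. Section 8.4.1 offers two end points joined by a bare *or*, and one of them is the EOS/FU visit. For subjects who stop early without progression, the Table 1.1 footnotes put End of Study at different times. Two sites could close SAE recording at different dates for otherwise identical subjects, and this group can include people who stopped because of an adverse event (Section 7.1).

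**Working it through.** **Inputs (protocol Section 1.3, Table 1.1)**
- Month: 30 days (table note).
- Call: 1 month after EOT (footnote b), tolerance −7 to +7 days (window row).
- EOT: day 0 to 7 after the last dose (footnote a).
- Additional MRI: 3 months = 90 days, ± 14, after the last dose (footnote e).

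**Step 1. Nominal timing.** Call day after last dose = EOT day + 30.
- EOT on day 0: 0 + 30 = day 30.
- EOT on day 7: 7 + 30 = day 37.

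With no tolerance used, the stated 30 days are covered.

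**Step 2. Permitted range.** Call day = EOT day + 30 + tolerance.
- Earliest: 0 + 30 − 7 = day 23.
- Latest: 7 + 30 + 7 = day 44 (later still if EOT is delayed as footnote a allows).

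**Step 3. Shortfall by EOT day.** Maximum uncovered days = 30 − (EOT day + 23) = 7 − EOT day, floored at zero.

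| EOT day | Earliest call | Maximum days uncovered |
|---|---|---|
| 0 | 23 | 7 |
| 1 | 24 | 6 |
| 2 | 25 | 5 |
| 3 | 26 | 4 |
| 4 | 27 | 3 |
| 5 | 28 | 2 |
| 6 | 29 | 1 |
| 7 or later | 30 or later | 0 |

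The worst case is 7 of 30 days (7/30 = 23%). There are 8 EOT days × 15 tolerances = 120 permitted combinations, of which 7 + 6 + 5 + 4 + 3 + 2 + 1 = 28 put the call before day 30. That is a count of what the schedule allows, not a probability.

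**Step 4. Other tables.** Table 1.3 uses the same 1-month post-EOT call but, as available, prints no tolerance for it. Without one the call falls on day 30 to 37 and no gap is shown. In Table 1.2 the call follows the last study visit of a treatment-free subject, so the question does not arise in that form.

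**Step 5. End of Study for subjects who stop early without progression.**
- Footnote b: day 23 to 44.
- Footnote e: after an MRI at 90 − 14 = day 76 to 90 + 14 = day 104, if no new therapy comes first.
- Difference: between 76 − 44 = 32 and 104 − 23 = 81 days, under that condition.

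**Step 6. The SAE cut-off.** Section 8.4.1 can be read as 30 days after the last dose for dosed subjects and EOS/FU for those with no study dose, as whichever of the two applies, or as 30 days after EOS/FU. No order of precedence is given.

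**The case against.** **The window is covered as scheduled.** This stands for nominal timing. A gap needs both an EOT visit on day 0 to 6 and use of the negative tolerance. The duty in Section 8.4.1 to record events to day 30 also holds whatever the date of the call. What is missing is a scheduled contact at or after day 30. The weekly calls in Section 6.2.2 do not clearly supply one, because they are reminders about bottles and diaries and collection of AEs on them is optional.

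**Footnote e is an exception, not a contradiction.** This largely stands. It opens by restricting itself to one subgroup, and the last-contact definition in Section 4.1.2 fits both footnotes. But footnote b carries no exception, so the reader has to supply it.

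**A reader might infer that an SAE on, say, day 50 is in or out depending on the footnote used.** The documents do not establish that. If the words about applicability in Section 8.4.1 separate dosed from treatment-free subjects, a day-50 SAE in a dosed subject is outside under either footnote. The wording is unclear; a discrepancy in data is not shown.

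**A reader might infer that late toxicity is undercounted, liver injury in particular.** That is not supported as a measured bias. Section 2.3 places the onset of cholestasis in the first 8 weeks of treatment, and its remark about a protracted course concerns events already under way. Subjects stopping for liver findings have repeated liver tests (Table 6.3), and SAEs are followed to resolution or stabilisation (Section 8.4.1). The study is descriptive, and the documents give no rate from which to size a loss.

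**A reader might infer that Section 9.5.2 promises collection of related events after day 30.** It classifies events that have been collected; it does not promise to collect them. A rule to record related events up to database lock would be optional.

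**Conclusion.** The point holds in limited form. In Table 1.1 the last scheduled AE contact may fall as early as day 23 after the last dose, so the 30-day window in Sections 8.4.1 and 9.5.2 is not guaranteed to be covered. The shortfall is 0 to 7 days, depending on the EOT day and the tolerance used, and zero at nominal timing. It is not shown for Table 1.3.

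Separately, the End of Study footnotes differ for subjects who stop early without radiologic progression, and Section 8.4.1 does not say which end point governs SAE collection. This is an ambiguity to resolve, not a demonstrated error in any count.

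The figures assume that EOT is never before the last dose (footnote a) and that a month is 30 days. If the ±7 days on the EOT column were read relative to the last dose, the earliest call would be −7 + 30 − 7 = day 16, but footnote a does not support that reading. The day 76 to 104 range assumes no new TGCT therapy before the MRI.

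**What to change.** 1. In Table 1.1, anchor the AE call to the last dose and hold it no earlier than day 30, for example 30 days with a window of 0/+7. Use the same anchor in Table 1.3. Where EOT is itself delayed under footnote a, word the upper limit so that the call still follows EOT.
2. In footnote b, name footnote e (f in Table 1.3) as the exception, consistent with Section 4.1.2.
3. In Section 8.4.1, state a single SAE cut-off for dosed subjects, reaching at least day 30 so that it matches Section 9.5.2, and a single one for treatment-free subjects.
4. As an editorial point, reconcile the Table 1.1 comment "Full PE on Screening and EOS, abbreviated PE at other visits" with the schedule, where End of Study is a phone call and the physical examination is marked in the EOT column.

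The cost is a few footnotes and one sentence. The earliest permitted call moves from day 23 to day 30, which is about a week at most, and no visit is added. Slightly more events may be recorded.

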2. Subjects who choose to discontinue pexidartinib treatment will be enrolled into the Treatment-Free period of the **Treatment-Free/Re-Treatment Cohort**. The assessments from the subject's End-of-Treatment visit from their prior study (eg, tumor assessments, PRO measures, and safety parameters) will serve as the Baseline measurements for PL3397-A-U4003 study. Subjects will discontinue pexidartinib treatment and undergo clinical assessments at 3-month intervals during the Treatment-Free period. Re-treatment with pexidartinib will be based on the discretion of the subject and Investigator. Tumor assessment, subjective and/or functional measures, and safety will be considered in the decision-making process. The rationale for discontinuing and restarting pexidartinib re-treatment will be recorded accordingly.

Subjects in the **Treatment-Free/Re-Treatment Cohort** who enter the Re-Treatment period will be administered pexidartinib at the dose at which they completed the prior study. Dosing is required on an empty stomach (at least

1 hour before or 2 hours after a meal or snack), at approximately the same times of the day, and approximately 12 hours apart. During the Re-Treatment period, Investigators will ensure weekly liver monitoring tests for the first 8 weeks (2 months), then every 2 weeks for 1 month, then once every 3 months or more frequently as directed by the Investigator.

The Investigator will evaluate the MRI scans every 6 months for subjects in the Treatment Continuation Cohort and every 3 months for subjects in the Treatment-Free/Re-Treatment Cohort to perform a qualitative tumor assessment (i.e., stable disease) for subjects in the Treatment Continuation Cohort. Additional imaging assessments may be performed with changes in tumor response(s) as deemed necessary by the Investigator.

Patient Reported Outcomes (PROs) measures will be performed at 3-month intervals for all subjects.

Ongoing safety assessment, laboratory assessments (serum chemistry and hematology), and physical examination will be performed at 3-month intervals and monitored for adverse events (AEs). Note that laboratory assessments for urinalysis will be performed at 6-month intervals.

See [Figure 1.1](#) for the study flow diagram.

Study Duration

The study start is the date when the first subject has signed the informed consent. Subjects will be evaluated for eligibility at the last visit of their prior study.

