Treatment Response/ Disease Assessment	MRI of affected joint	X ^e		X	X	X	X	X ^f		Tumor assessment. Additional imaging assessments may be performed with changes in tumor response(s) as deemed necessary by the Investigator.
Dosing Diary	Provide Diary		X	X	X	X	X			Diary for pill count and AEs between scheduled clinic visits
	Review Diary			X	X	X	X	X		
	Dispense 3-month supply	X		X	X	X	X			A drug supply for more than 3 months may be dispensed.
Study Drug: Pexidartinib	Collect Returned/ Assess Treatment Compliance			X	X	X	X	X		
EOS Form									X	

AE = adverse event; BL = baseline; D = day; ECG = electrocardiogram; EOS = End of Study; EOT = End-of-Treatment; EQ-5D-5L = European Quality of Life Five Dimension Five Level Scale; FSH = follicle stimulating hormone; FU = Follow-up; M = month; MRI = magnetic resonance imaging; PRO = Patient-Reported Outcome; PROMIS PF = Patient-Reported Outcomes Measurement Information System – Physical Function; SAE = serious adverse events; SCR = screening; TEAE = treatment emergent adverse events; TVS = tumor volume score.

Note: For all visits, a month is considered a 30-day interval, except for the M1/M2 visit for re-treatment patients where there is a 28-day window.

^a Pexidartinib will be administered at the dose at which subject completed the prior study. Doses will be taken on an empty stomach (at least 1 hour before or 2 hours after a meal or snack), at approximately the same times of the day, and approximately 12 hours apart. Weekly liver monitoring tests for the first 8 weeks, then every 2 weeks for 1 month, then every 3 months or more frequently as directed by the Investigator.

^b Patient visits should be done every 3 Months until 21 Months after baseline. The combined overall study duration of all treatment, treatment-free, and re-treatment phases should not exceed 24 months.

^c The EOT visit should occur within 7 days after the last dose of pexidartinib or at the time the decision is made to discontinue pexidartinib (if this is more than 7 days after the last dose of pexidartinib), unless there is a medical condition that prevents subjects from completing the visit within this time.

^d The End-of-Study will be reached with a follow-up phone call 1-month post-EOT visit to collect AE information.

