^e BL2 MRI will need to be done within 14 days before treatment BL2 (window -14 days). Response should note “Progression” for those patients re-starting treatment. Assessments after re-treatment should use BL2 as the reference to determine Progression or Non-Progression.

^f Only subjects who end their study participation early with no radiologic disease progression will have an additional MRI at 3 months \pm 14 days after their last dose of study treatment or before any new TGCT therapy, including surgery, whichever occurs first. EOS will occur after this additional MRI.

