For subjects who restart pexidartinib treatment in the Re-Treatment period of the **Treatment-Free/Re-Treatment Cohort**, pexidartinib will be administered at the dosage level at which the subject completed the prior study. Doses must be administered on an empty stomach (at least 1 hour before or 2 hours after a meal or snack), at approximately the same times of the day, and approximately 12 hours apart. The full set of study assessments will be performed (Baseline-2). During re-treatment, Investigators will ensure weekly liver monitoring tests for the first 8 weeks, then every 2 weeks for the next month, then every 3 months or more frequently as directed by the Investigator (see [Table 6.3](#)).

The Investigator will evaluate the quarterly magnetic resonance imaging (MRI) scans to perform a qualitative tumor assessment (i.e., stable disease) for subjects in the **Treatment-Free/Re-Treatment Cohort**. Additional assessments may be conducted based on worsening of tumor response as deemed necessary by the Investigator. For those subjects who restart pexidartinib treatment in the Re-Treatment period of the **Treatment-Free/Re-Treatment Cohort**, the response should note “Progression” and the assessments after re-treatment should use Baseline 2 as the reference to determine Progression or Non-Progression.

The PROs (PROMIS PF and EQ-5D-5L) will be performed every 3 months for all subjects.

Ongoing safety will include serum chemistry, hematology, urinalysis, coagulation, ECG, hormone testing, and physical examination, and subjects will be monitored for adverse events (AEs)/TEAEs.

Subjects on treatment who end their study participation early with no radiologic disease progression will undergo a final MRI 3 months \pm 14 days after their last dose of study treatment or before any new TGCT therapy, including surgery.

Subjects who discontinue early from the study will complete the End-of-Study (EOS)/EOT visit and will be withdrawn from the study.

The subject population is described in [Section 5](#). A flow diagram of the study is presented in [Figure 1.1](#).

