7.1. Subject Withdrawal/Discontinuation from the Study

Subjects may discontinue from the study for any of the following reasons:

- Completed
- Complete Response
- Death
- Adverse Event
- Progressive Disease
- Clinical Progression
- Lack of Efficacy
- Withdrawal by Subject (to discontinue study drug)
- Physician Decision
- Lost to Follow-up (see Section [7.2](#) for details on when a subject is considered Lost to Follow-up)
- Pregnancy
- Protocol Deviation
- Study Termination by Sponsor
- Other

If the reason for study discontinuation is the death of the subject, the options for categorizing the primary cause of death are progressive disease or adverse event. If reason of death is unknown, every effort should be made to obtain the primary cause of death. Only 1 AE will be recognized as the primary cause of death.

Only subjects who refuse all of the following methods of follow-up will be considered to have withdrawn consent from study participation (i.e., from the interventional portion and follow-up):

- Attendance at study visits per protocol
- Study personnel contacting the subject by telephone
- Study personnel contacting an alternative person
- Study personnel accessing and reviewing the subject's medical information from alternative sources

If the subject refuses all of the above methods of follow-up, the Investigator should personally speak to the subject to ensure the subject understands all of the potential methods of follow-up. If the subject continues to refuse all potential methods of follow up, the Investigator will document this as a withdrawal of consent (from the interventional portion and follow-up).

Withdrawal Procedures

If a subject is withdrawn from the study:

- The Investigator will complete and report the observations as thoroughly as possible up to the date of withdrawal including the date of last dose, date of last contact, and the reason for withdrawal;
- If disclosure of future information is also withdrawn, the Sponsor may retain and continue to use any data collected before such a withdrawal of consent;
- The subject may request destruction of any samples taken and not tested, and the Investigator must document this in the site study records;
- Study site personnel may use local, regional, and national public records (in accordance with local law) to monitor vital status.

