CR	SD	SD provided minimum criteria for SD duration met, otherwise, PD
CR	PD	SD provided minimum criteria for SD duration met, otherwise, PD
CR	NE	SD provided minimum criteria for SD duration met, otherwise, PD
PR	CR	PR
PR	PR	PR
PR	SD	SD
PR	PD	SD provided minimum criteria for SD duration met, otherwise, PD
PR	NE	SD provided minimum criteria for SD duration met, otherwise, PD
NE	NE	NE

CR = complete response; PR = partial response; SD = stable disease; NE = not evaluable; PD = progressive disease

^a If a CR is truly met at first time point, then any disease seen at a subsequent time point, even disease meeting PR criteria relative to baseline, makes the disease PD at that point (since disease must have reappeared after CR).

Best response would depend on whether minimum duration for SD was met. However, sometimes ‘CR’ may be claimed when subsequent scans suggest small lesions were likely still present and in fact the patient had PR, not

CR at the first time point. Under these circumstances, the original CR should be changed to PR and the best response is PR.

Source: Eisenhauer EA, Therasse P, Bogaerts J, et al. New response evaluation criteria in solid tumours: Revised RECIST guideline (version 1.1). Table 3. Euro J of Can. 2009;45:228-47

Special Notes on Response Assessment

When nodal disease is included in the sum of target lesions and the nodes decrease to 'normal' size (< 10 mm), they may still have a measurement reported on scans. This measurement should be recorded even though the nodes are normal in order not to overstate progression should it be based on increase in size of the nodes. As noted earlier, this means that subjects with CR might not have a total sum of '0' on the eCRF.

Subjects with a global deterioration of health status requiring discontinuation of pexidartinib without objective evidence of disease progression at that time should be reported as 'clinical progression.' Every effort should be made to document objective progression even after discontinuation of treatment. Symptomatic deterioration is not a descriptor of an objective response: it is a reason for stopping study drug. The objective response status of such subjects is to be determined by evaluation of target and non-target disease. If a radiographic tumor assessment has not been performed within 4 weeks of the time of clinical progression, then another radiographic assessment should be performed without waiting for the next regularly scheduled scan.

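### Every restart is to be recorded as tumour progression, whatever the MRI taken just before restart shows

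*Combined protocol and SAP*

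**What the plan says.** Table 1.3 (Section 1.3) schedules an MRI of the affected joint at BL2, in the row for treatment response and disease assessment. Footnote e on that cell requires the scan in the 14 days before BL2 and then states: "Response should note “Progression” for those patients re-starting treatment". Section 4.1.1 gives the same instruction for the Re-Treatment period: "the response should note “Progression” and the assessments after re-treatment should use Baseline 2 as the reference to determine Progression or Non-Progression". Neither text ties the entry to the finding on the scan.

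The decision to restart is discretionary. The synopsis says "Re-treatment with pexidartinib will be based on the discretion of the subject and Investigator", and Sections 4.1.1 and 8.3.3 also rest it on discretion. The synopsis and Section 4.1.1 list the matters to be weighed: the state of the tumour, how the subject feels and functions, and safety. They also require the reason for restarting to be recorded. No section sets a radiologic threshold for restart.

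Section 9.5.1.2 plans a descriptive summary of the qualitative tumour assessments in re-treated subjects. It does not say whether the BL2 entry is part of that summary.

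**The concern.** The instruction fills a tumour-response entry from a treatment decision. A subject who restarts because of symptoms, or by preference, with an unchanged BL2 scan is entered as progressed. The entry then says only that the subject restarted, which is already known.

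Section 2.2 names the effect of stopping drug in people with stable or residual disease as the gap this study is meant to fill. Whether the tumour had regrown by the time of restart is central to that question. Section 4.2 also assumes that re-treatment will stabilise the disease again. A tumour that was stable before and after restart would read *Progression* at BL2 and *Non-Progression* afterwards. That looks like re-stabilisation, but the recording rule alone has produced it.

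**Working it through.** The documents state no figure on this point, so there is none to reproduce. The check compares the texts and then sizes the effect.

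**1. The recording rule against the restart rule.** The rule applies to all who restart, and the post-restart call uses BL2 as its reference. Suppose the tumour then stays unchanged from BL2:

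| Situation at restart | BL2 entry by rule | Entry from the scan | Later entry |
|---|---|---|---|
| Regrowth on MRI | Progression | Progression | Non-Progression |
| Stable MRI, worse symptoms or function | Progression | Not progressed | Non-Progression |
| Stable MRI, no clinical worsening, subject's wish | Progression | Not progressed | Non-Progression |

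The recorded sequence is the same in all three rows, so it cannot separate them.

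**2. Could the word cover clinical progression?** It is not defined in footnote e or Section 4.1.1, so that reading is open. Elsewhere the protocol keeps the ideas apart:
- Footnote f of the same table specifies the radiologic kind: "Only subjects who end their study participation early with no radiologic disease progression".
- Section 7.1 lists "Clinical Progression" as a separate item from progressive disease.
- Section 10.4, writing about stopping drug, says "Symptomatic deterioration is not a descriptor of an objective response: it is a reason for stopping study drug".
- The defined criteria are imaging-based: an increase of at least 30% in tumour volume score (Section 8.3.3), or of at least 20% and 5 mm in the sum of diameters (Section 10.4).

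The wider reading would make the second row of the table acceptable but would mix regrowth with symptoms. The third row stays wrong on either reading.

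**3. Size of the distortion.** Let n be the number of restarters and k the number without progression. Neither is in the documents.
- Share entered as *Progression* at BL2 = n/n = 100%.
- Share the scans would give = (n − k)/n.
- Overstatement = 100 × k/n percentage points.
- For k = 1: n = 5 gives 20 points, n = 10 gives 10, n = 20 gives 5.
- For an assumed k/n between 0 and 50%, the overstatement runs from 0 to 50 points.

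**4. Can the treatment-free scans stand in for the BL2 read?** Table 1.2 uses 30-day months and ±14-day windows for the three-monthly visits.
- Earliest M3 = 90 − 14 = day 76.
- Latest M6 = 180 + 14 = day 194.
- Largest gap between these two scheduled scans = 194 − 76 = 118 days (nominal 90).

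If the BL2 scan falls at or just before the later visit, the previous scheduled scan can be up to 118 days old. It shows the tumour at an earlier date and replaces the BL2 read only in part.

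**The case against.** The best defence is that this is a deliberate convention. Section 4.2 builds the design on pausing drug until the disease shows signs of advancing, so a restart is taken to mean progression. That is a design assumption, however, and no section makes it a condition for restart.

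It can also be argued that the entry is a reason code and not a scan read. The summary of changes describes the edit in terms that allow this. The current text says the response is to be noted, and the footnote sits on the MRI cell, so the tumour-response reading is the natural one. The eCRF would settle how the entry is stored.

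Several limits on the harm do stand:
- The primary analysis (Section 9.5.1.1) counts resumption of drug itself as the event and does not use the label.
- Later calls use BL2 as reference, so the label does not change them.
- Tumour assessment is a listed objective for the Re-Treatment period and not for the Treatment-Free period. Whether any planned summary uses the BL2 entry is unstated, and details are left to the SAP.
- The rationale is recorded and treatment-free MRIs are taken. Retained scans may be read centrally, although that is optional.
- Restart is considered at scheduled visits that include an MRI, so the visit scan may also serve as the BL2 scan, and its read may survive in the visit record. The 118 days is the extreme pairing of windows.
- Safety is listed only as a consideration and may well weigh against restarting.
- The study is descriptive, with no hypothesis test.

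These points bound the consequence. They do not make the entry correct for a restarter with a stable scan.

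**Conclusion.** The concern holds. Followed exactly, footnote e and Section 4.1.1 enter a wrong tumour response for any restarter whose BL2 scan shows no progression. This is an error in the rule as written and not merely missing detail.

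Its size depends on the share of restarters without progression, which the documents do not give; the n of 5 to 20 and the 0 to 50% range above are assumptions. What is exposed is the response recorded at restart and, if BL2 entries are counted, the descriptive tumour summary in re-treated subjects. If the eCRF holds a separate field for the scan read, the information survives and the harm falls to a misleading label. The point should be fixed, but it does not threaten the primary result. Confidence is high on the wording and lower on the practical harm.

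**What to change.** - In Table 1.3 footnote e and Section 4.1.1, replace the automatic entry with the investigator's actual read of the BL2 MRI against a named comparator. Study Baseline and the lowest treatment-free assessment are two candidates; the sponsor should choose one and state it.
- Keep the restart rationale, including any clinical progression, in a separate field.
- In Section 9.5.1.2, state that BL2 is the re-treatment baseline and is not counted as a response to re-treatment.
- For BL2 entries already made, check them against a separate scan read where one is on record. Where none exists, flag the entry as set by rule.
- As a minor cross-reference, say in Sections 8.3.3 and 10.4 that Re-Treatment calls use the BL2 reference. Section 8.3.1 points to Section 10.4, where progression is measured from the smallest value on study.

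The cost is a small protocol and eCRF wording change plus a limited data check. The scan and the rationale are already required, so no new scan, reader or clinical rule is involved.
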